### 5.1.3 Provision, storage and dispensing

The central distribution pharmacy will distribute the labeled study medication to the trial sites. The sites will be supplied with venetoclax supply sufficient for one full cycle of V-MAC for one patient after initiation of the study. Sites are responsible for contacting the drug distribution center to order study drug for further treatment of individual patients in the trial. Sites will complete the Drug Request Form available in the ISF. The form will be faxed or emailed to the sponsor's drug distribution center. The faxes/emails are processed during regular business hours, Monday to Friday 08:00 am to 05:00 pm.

#### Storage and dispensing

Blister packs and bottles should be stored at 15-25°C. After dispensing to the patient, venetoclax may be stored at home at room temperature (below 25°C) for as long as patient's study participation.

The site's investigator is responsible for ensuring the correct storage and sufficient stocks of the IMP at the site.

#### 5.1.4 Drug accountability

The investigator has to ensure that the investigational medicinal product (IMP) is only used according to this protocol.

- The investigator bears the responsibility for the proper storage in an appropriate place to which unauthorised persons have no access and storage conditions are kept.
- The investigator must only dispense the IMP to subjects who have been enrolled in the study. The dispensing of the IMP to subjects outside of this clinical trial is not permitted.
- The investigator, or an individual who is designated by the investigator per delegation log, should explain the correct use of the IMP to each trial subject and check at regular intervals that each subject is following the instructions correctly.

#### Investigational medicinal product Stock Lists (Drug Accountability)

The investigator or pharmacist or another appropriate individual who is designated by the investigator, should maintain records of the stocks of the IMP, the use by the individual trial subjects, and the return of unused investigational medicinal products to the trial centre or its disposal.

- Each delivery will be documented in writing on the forms provided and the forms will be returned to the Drug Distribution Center stated as an acknowledgement of receipt.
- Complete documentation of the whereabouts of the IMP (incoming/outgoing) on appropriate forms is mandatory. These records should include dates, quantities, batch numbers, expiry dates (if applicable) and the unique code numbers assigned to the IMP and the trial subjects. The investigator should maintain records that document adequately that the subjects received the doses specified by the protocol. These records should be checked against all delivery notes received from AbbVie.
- Any discrepancies between stock and drug account have to be explained.
- The Investigator is responsible for destroying any unused, partially used and empty blisters/bottles of IMP after the clinical monitor has approved the drug accountability logs. This process should be documented appropriately. A confirmation of the destruction will be filed in Investigator's Site File and also in the TMF.

The patients should document the administration of the study drug in a patient diary which will be provided from the sponsor.

## 5.2 Cytarabine

Commercially available cytarabine will be given and provided locally.

For information on the formulation, packaging, and handling of cytarabine see the summary of product characteristics (SmPC) for cytarabine as used in standard practice.

Cytarabine will be defined as Investigational medicinal product (IMP) for Phase I/ Escalation Phase only, in Phase II/ Expansion Phase, it will be given as concomitant medication.

## 5.3 Mitoxantrone

Mitoxantrone will be given as concomitant medication and supplied locally. For information on the formulation, packaging, and handling of mitoxantrone see the the SmPC for mitoxantrone as used in standard practice.

## 5.4 Dosing and administration

The treatment plan combines a fixed dose of venetoclax and mitoxantrone with increasing doses of cytarabine (V-MAC). Patients will be admitted to the hospital for at least the first week of study treatment.

### 5.4.1 Treatment schedule in dose escalation part of the study (phase I)

The treatment schedule will be as follows:

Table 1: Treatment schedule in the dose escalation part

Dose level	Venetoclax target dose QD	Cytarabine dose	Mitoxantrone dose QD
-1	50-400 mg PO, days 1-10	100 mg/m  IV CI, days 4-10	10 mg/m  IV, days 6-8
1	50-400 mg PO, days 1-14	200 mg/m  IV CI, days 4-10	10 mg/m  IV days 6-8
2	50-400 mg PO, days 1-14	500 mg/m  IV BID, days 4-6	10 mg/m  IV days 6-8
3	50-400 mg PO, days 1-14	1000 mg/m  IV BID, days 4-6	10 mg/m  IV days 6-8

[figure not shown]

Figure 2: Treatment schedule

### Venetoclax

**Day 1 of venetoclax will define the study treatment start.** To mitigate the potential risk of TLS, venetoclax administration will start with a pre-specified dose ramp-up to reach the target dose level of 400 mg at day 4 (refer to Table 2).

Table 2: Venetoclax ramp up

Day	Venetoclax dose
1	50 mg
2	100 mg
3	200 mg
4 – 14 (10)*	400 mg

\* Venetoclax will be administered until day 14, only at dose level -1, venetoclax will be given until day 10.

Each dose of venetoclax should be taken with approximately 240 ml of water within 30 minutes after the completion of a meal, preferably breakfast. The dose should be administered at the same time each day. On days with planned cytarabine administration, venetoclax must be given prior to cytarabine and mitoxantrone. If a patient develops any lab changes suggestive of TLS within the first 24 hours after either first dose or during ramp up, venetoclax should be withheld until normalization of lab changes. Venetoclax will be administered in Phase I and II no longer than 10/14 days except during maintenance therapy.

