##### TLS Prophylaxis and Management in Escalation part:

TLS prophylaxis must be initiated in all such subjects prior to the first venetoclax dose or first new escalated dose as described below.

- Hospitalization (required) starting the night before the first dose of venetoclax and for a minimum of 24 hours after reaching the target dose of 400 mg venetoclax.
- An oral agent to reduce the uric acid level (e.g., allopurinol) to be initiated at least 72 hours prior to dosing. Treatment may need to be continued for up to 28 days based on the ongoing risk of TLS development. Subjects allergic to or otherwise unable to receive allopurinol must use another uric acid reducer starting at least 72 hours prior to dosing or rasburicase on the day of treatment (prior to venetoclax dosing).
- Oral hydration (approximately 1.5 to 2 liters as tolerated) per day starting from at least 24 hours prior to first dose or any dose escalation during ramp up.
- Intravenous hydration must be started upon admission or the night prior to beginning treatment with a target of approximately 2 L per day or as clinically appropriate and continued during

hospitalization. Urine output must be monitored. Diuretics may be used per investigator discretion.

- TLS chemistry tests on the first day of venetoclax dosing and each day of a new dose at pre-dose (within 4 hours prior to dosing), 6-8 hours and 24 ( $\pm$  2) hours post-dose. Additional laboratory assessments may be performed, per investigator discretion, post-dose during ramp up and up to 48 hours after reaching the target dose if clinically indicated.
- TLS chemistry test results (calcium, inorganic phosphorus, potassium, uric acid, and creatinine) must be reviewed by the investigator in real time and prior to the subject's next dose of venetoclax to ensure appropriate subject management.
- If any clinically significant laboratory changes are observed within the first 24 hours after initiation of dosing or after a dose escalation during ramp up, see [Appendix 2](#) (Recommendations for Initial Management of Electrolyte Abnormalities and Prevention of Tumor Lysis Syndrome [TLS]) for management guidelines. Refer to table in [Appendix 3](#) for definitions of laboratory and clinical TLS.
- If a subject meets criteria for clinically significant laboratory TLS, no additional venetoclax dose should be administered until resolution.

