  - Prophylactic reductions of potassium, inorganic phosphorus and/or uric acid above normal range prior to beginning dosing are recommended.

For continued dosing of venetoclax, monitor for evidence of TLS during treatment, and manage abnormalities in serum creatinine, uric acid and electrolytes promptly. For subjects at higher risk (i.e., circulating blasts), more intensive measures should be considered. Refer to [Appendix 2](#) for a special sample handling procedure that must be followed to avoid ex vivo uric acid degradation in the presence of rasburicase.

If the chemical changes and laboratory TLS have not resolved within 24 hours, the continuation of venetoclax has to be discussed between the investigator and the Coordinating Investigator.

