#### TLS Prophylaxis and Management in the Expansion part

Safety data from the 94 subjects treated in 3 AML studies demonstrated no events of TLS; 32 subjects in monotherapy study (Study M14-212) and 22 subjects in a combination study (Study M14-387) using low dose cytarabine. Based on this data, simplification of TLS prophylaxis and management will be followed for subjects enrolled into the expansion stage.

All subjects enrolled into the expansion part will need TLS prophylaxis and monitoring. The minimum requirements for TLS prophylaxis and management for subjects enrolled into the

expansion part are shown below. All other prophylaxis and monitoring procedures for TLS will be done as per institutional/regional standards:

- All subjects will be hospitalized on or before Day 1 of study treatment (V-MAC) prior to administration of the first dose of study venetoclax and remain in the hospital at least for 24 hours after reaching the target dose of 400 mg venetoclax.
- Administration of uric acid reducing agent, adequate oral and intravenous hydration while monitoring the fluid status of the subject prior to and during the ramp up of venetoclax will be based on regional standards or institutional guidelines.
- TLS chemistry tests are to be drawn (calcium, inorganic phosphorus, potassium, uric acid, and creatinine) on the first day of venetoclax dosing and on each day of a new dose at pre-dose (within 4 hours prior to dosing), 6-8 and 24 ( $\pm$  2) hours post dose. Additional laboratory assessments may be performed, per investigator discretion, post-dose during ramp up and up to 48 hours after reaching target dose if clinically indicated.
- Abnormal chemistry test results should be corrected promptly.
- If a subject meets criteria for clinically significant laboratory or clinical TLS, no additional venetoclax dose should be administered until resolution.
  - Prophylactic reductions of potassium, inorganic phosphorus and/or uric acid above normal range are recommended prior to beginning study treatment and continue based on the ongoing risk of TLS.

For continued dosing of venetoclax, monitor for evidence of TLS during treatment, and manage abnormalities in serum creatinine, uric acid and electrolytes promptly. For subjects at higher risk (i.e., circulating blasts), more intensive measures should be considered.

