### Recommendations for Initial Management of Electrolyte Imbalances and Prevention of Tumor Lysis Syndrome (TLS)

Abnormality	Management Recommendations
Hyperkalemia (including rapidly rising potassium)	
Potassium $\geq 0.5$ mmol/L increase from prior value (even if potassium within normal limits [WNL])	
 
Recheck potassium, phosphorus, uric acid, calcium and creatinine in 1 hour STAT. If further <math>\geq 0.2</math> mmol/L increase in potassium, but still <math><</math> upper limit of normal (ULN), manage as per potassium <math>\geq</math> ULN. Otherwise recheck in 1 hour.
 
Resume per protocol testing if change in potassium is <math>< 0.2</math> mmol/L, and potassium <math><</math> ULN, and no other evidence of tumor lysis.
 
At discretion of investigator, may recheck prior to hospitalization. If stable or decreased, and still WNL, hospitalization is at the discretion of the investigator. Potassium, phosphorus, uric acid, calcium and creatinine must be rechecked within 24 hours.
 

Potassium $>$ upper limit of normal	
 
Perform STAT ECG and commence telemetry.
 
Nephrology (or other acute dialysis service) notification with consideration of initiating dialysis.
 
Administer Kayexalate 60 g (or Resonium A 60 g).
 
Administer furosemide 20 mg IV <math>\times 1</math>.
 
Administer calcium gluconate 100 – 200 mg/kg IV slowly if there is ECG/telemetry evidence of life-threatening arrhythmias.
 
Recheck potassium, phosphorus, uric acid, calcium and creatinine in 1 hour STAT.
 
If potassium <math><</math> ULN 1 hour later, repeat potassium, phosphorus, uric acid, calcium and creatinine 1, 2 and 4 hours, if no other evidence of tumor lysis.
 

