### Definitions of Laboratory and Clinical Tumor Lysis Syndrome\*

Metabolic Abnormality	Criteria for Classification of Laboratory Tumor Lysis Syndrome	Criteria for Classification of Clinical Tumor Lysis Syndrome
Hyperruricemia	Uric acid > 8.0 mg/dl (475.8 µmol/liter) in adults or above the upper limit of the normal range for age in children	
Hyperphosphatemia	Phosphorus > 4.5 mg/dl (1.5 mmol/liter) in adults or > 6.5 mg/dl (2.1 mmol/liter) in children	
Hyperkalemia	Potassium > 6.0 mmol/liter	Cardiac dysrhythmia or sudden death probably or definitely caused by hyperkalemia
Hypocalcemia	Corrected calcium < 7.0 mg/dl (1.75 mmol/liter) or ionized calcium < 1.12 (0.3 mmol/liter) †	Cardiac dysrhythmia, sudden death, seizure, neuromuscular irritability (tetany, paresthesias, muscle twitching, carpopedal spasm, Trousseau's sign, Chvostek's sign, laryngospasm, or bronchospasm), hypotension, or heart failure probably or definitely caused by hypocalcemia
Acute kidney injury ‡	Not applicable	Increase in the serum creatinine level of 0.3 mg/dl (26.5 µmol/liter) (or a single value > 1.5 times the upper limit of the age-appropriate normal range if no baseline creatinine measurement is available) or the presence of oliguria, defined as an average urine output < 0.5 mL/kg/hr for 6 hrs

† The corrected calcium level in milligrams per deciliter = measured calcium level in milligrams per deciliter + 0.8 × (4-albumin in grams per deciliter).

‡ Acute kidney injury is defined as an increase in the creatinine level of at least 0.3 mg per deciliter (26.5 µmol per liter) or a period of oliguria lasting 6 hours or more. By definition, if acute kidney injury is present, the patient has clinical tumor lysis syndrome.

Note: In laboratory tumor lysis syndrome, two or more metabolic abnormalities must be present during the same 24-hour period within 3 days before the start of therapy or up to 7 afterward. Clinical tumor lysis syndrome requires the presence of laboratory tumor lysis syndrome plus an increased creatinine level, seizures, cardiac dysrhythmia, or death.

\* Howard SC, Jones DP, Pui CH. The tumor lysis syndrome. N Engl J Med. 011;364(19):1844-54.

## Appendix 4

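### Sections 5.4.1 and 5.4.5 set different triggers and different release conditions for withholding venetoclax in the same ramp-up window

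*Protocol*

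**What the plan says.** Section 5.4.1 (Venetoclax), below the ramp-up table, gives the trigger as "If a patient develops any lab changes suggestive of TLS within the first 24 hours after either first dose or during ramp up" and the action as "venetoclax should be withheld until normalization of lab changes". It states no threshold, no number of analytes and no cross-reference to section 5.4.5.

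Section 5.4.5, escalation part, works in steps:

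- The first step begins "If any clinically significant laboratory changes are observed within the first 24 hours after initiation of dosing or after a dose escalation during ramp up" and refers the investigator to Appendix 2 for management and to Appendix 3 for definitions.
- The hold comes next: "If a subject meets criteria for clinically significant laboratory TLS, no additional venetoclax dose should be administered until resolution".
- Persisting cases have their own rule: "If the chemical changes and laboratory TLS have not resolved within 24 hours, the continuation of venetoclax has to be discussed". The Coordinating Investigator is a party to that discussion.

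Appendix 2 lists laboratory changes and the response to each. The mildest potassium entry is a rise of 0.5 mmol/L or more, even when the value is still normal. No entry mentions withholding venetoclax. Appendix 3 defines the syndrome: "In laboratory tumor lysis syndrome, two or more metabolic abnormalities must be present during the same 24-hour period".

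For the expansion part, section 5.4.5 words the hold as "If a subject meets criteria for clinically significant laboratory or clinical TLS, no additional venetoclax dose should be administered until resolution". It also allows an interruption of up to 72 hours after transient changes without a dose reduction.

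**The concern.** The ramp-up is the protocol's stated measure against TLS, so the rule for interrupting it should read the same wherever a site looks. Here a site working from the dosing section and a site working from the TLS section can treat the same laboratory result differently.

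There is also a route into the analysis sets. Section 5.4.1 limits venetoclax to 14 days (10 at dose level -1), so held days are not added at the end. Section 3.2.1 requires at least 3800 mg for DLT evaluability. Section 3.2 excludes TLS-type laboratory abnormalities from the DLT definition if they are adequately controlled within 7 days. A phase I patient held for such changes who falls below 3800 mg without a DLT is replaced (section 4.4.2) and does not enter the MTD analysis set (section 8.1.2.1). The per-protocol set in section 8.2.2.2 uses the same minimum.

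**Working it through.** **1. The two rules side by side (escalation part, ramp-up)**

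| | Section 5.4.1 | Section 5.4.5 with Appendices 2 and 3 |
|---|---|---|
| Change suggestive of TLS, short of laboratory TLS | Hold | Managed per Appendix 2; no hold stated |
| Clinically significant laboratory TLS | Hold | Hold |
| Release | Values normalised | Resolution; continuation discussed if unresolved at 24 hours |

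The rules agree in the second row and differ in the first and third. The term clinically significant laboratory TLS has no definition beyond Appendix 3.

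**2. How many patients fall in the first row**

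The protocol gives no figure to reproduce. Its only TLS frequency is no events in 94 AML subjects (section 5.4.5, expansion part), which says nothing about the looser trigger. Only the direction follows from the definitions: laboratory TLS is a subset of suggestive changes, so section 5.4.1 holds at least as many patients.

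As an illustration by assumption only, take four analytes, each abnormal with probability p and independent of the others. Then P(at least one) = 1 - (1-p)^4, and P(at least two) = 1 - (1-p)^4 - 4p(1-p)^3.

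| p | At least one | At least two | Gap in points |
|---|---|---|---|
| 2% | 7.8% | 0.2% | 7.6 |
| 5% | 18.5% | 1.4% | 17.1 |
| 10% | 34.4% | 5.2% | 29.2 |
| 20% | 59.0% | 18.1% | 40.9 |

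If abnormalities always occur together, the gap is 0. The range is therefore 0 to about 41 points. The model also ignores Appendix 3's condition that both abnormalities fall in the same 24 hours.

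**3. Exposure (14-day dose levels)**

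The planned total from Table 2 is 50 + 100 + 200 + 11 × 400 = 4750 mg. The margin above the minimum is 4750 - 3800 = 950 mg. The day-14 limit is kept throughout.

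*Ramp resumes where it stopped.* Each held day removes one 400 mg day from the end, so the total is 4750 - 400h for h held days:

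- 1 day: 4350 mg
- 2 days: 3950 mg
- 3 days: 3550 mg, below 3800 mg

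*Ramp follows the calendar.* Only the doses scheduled on held days are lost:

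- Days 2-4: 4750 - (100 + 200 + 400) = 4050 mg
- Days 2-5: 4750 - (100 + 200 + 400 + 400) = 3650 mg, below 3800 mg
- Days 3-5: 4750 - (200 + 400 + 400) = 3750 mg, below 3800 mg

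Two held days lose at most 800 mg, which is less than 950 mg, so a hold of one or two days never crosses the minimum on either reading. Three held days cross it if the ramp resumes where it stopped. On the calendar, three cross it if the hold starts on day 3 or later, and four are needed if it starts on day 2.

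**The case against.** The strongest reply is that the rules can both be obeyed. Section 5.4.5 does not say that dosing must continue below laboratory TLS, and it requires TLS chemistry to be reviewed before the next dose. A site that follows the broader rule breaks neither section, and a dose can stay held while continuation is discussed. This is correct, but it does not remove the problem. Section 5.4.5 separates laboratory changes from laboratory TLS and attaches the hold to the second, so a site relying on it could reasonably dose a patient whom section 5.4.1 holds.

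It can also be said that section 1.3.2 and the visit-schedule footnotes point to section 5.4.5 for TLS management. They do, but a pointer sets no precedence and does not withdraw the sentence in section 5.4.1.

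A third reply is that whether a change is suggestive of TLS is a matter of judgement, so one abnormal value is not automatically a hold under section 5.4.1. That stands, and the point is limited to changes judged suggestive.

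A reader might infer that the two rules lead to very different shares of patients with held doses, or that the choice between them largely decides who is evaluable. The documents support neither. The first needs rates that the protocol does not give, and a large gap appears only under independence and chosen values of p. The second overlooks that holds of one or two days leave the patient above 3800 mg, that patients with a DLT count whatever their dose, and that under-exposed phase I patients without a DLT are replaced.

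**Conclusion.** The inconsistency holds as a matter of text: one ramp-up window has two triggers and two release conditions, and nothing states which prevails. Its frequency is unknown, and only its direction can be derived.

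The consequence for exposure is limited to holds of at least three days. This rests on the 14-day limit being kept and on the 14-day dose levels; section 3.2.1 gives no minimum for dose level -1. Which three- or four-day holds cross 3800 mg depends on whether the ramp resumes or follows the calendar, which the protocol does not say. The limit in section 5.4.1 settles only that days are not added at the end.

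The analysis sets exposed are the phase I MTD set, through replacement, and the per-protocol sensitivity analysis. The phase II primary test of CR/CRi uses the full analysis set, which has no minimum dose, so it and its sample size of 42 are unaffected. The point should be corrected because it concerns a safety rule that sites may apply inconsistently, not because it threatens the primary conclusion.

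**What to change.** The sponsor should reconcile section 5.4.1 (Venetoclax), section 5.4.5 (escalation part) and Appendices 2 and 3 so that one trigger and one resumption condition apply during ramp-up, in the same words or by cross-reference. The expansion-part text of section 5.4.5, including the 72-hour interruption allowance, should be checked against the result. The protocol should also state whether, after a hold, the ramp resumes where it stopped or follows the calendar within the 10- or 14-day limit, so that exposure can be counted consistently against the 3800 mg minimum. The choice of clinical rule belongs to the sponsor.

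The cost is protocol wording, through the written amendment that section 12 requires. Sample size, endpoints and the primary analysis do not change.
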